### Appendix 3 Pharmacokinetic and Biomarker Sampling Schedule (cont.)

#### Post-Induction Treatment (Eligible FL Patients)

Study Visit	Serum Obinutuzumab PK Sample a, b	Plasma Idasanutlin PK and Serum MIC-1 Sample c	Plasma Venetoclax PK Sample
Month 1, Day 1	Pre-infusion (within 5 hr prior to dose)	—	—
Month 7, Day 1	Pre-infusion (within 5 hr prior to dose)	—	—
Month 13, Day 1	Pre-infusion (within 5 hr prior to dose)	—	—
Month 19, Day 1	Pre-infusion (within 5 hr prior to dose)	—	—
Post-treatment	—	—	—
Treatment discontinuation	Any time during visit	—	—
120 days after the last dose	Any time during visit	—	—
1–2 years after the last dose	Any time during visit (if patient is in the clinic)	—	—

FL=follicular lymphoma; PK=pharmacokinetic.

Note: A “—” indicates not applicable.

a Sample collection timing is relative to the specified drug.

b Samples collected for PK analysis may be used for additional PK, HAHA, and/or ATA assay development and validation, and additional immunogenicity characterization, at the discretion of the clinical pharmacologist and/or the clinical scientist.

c Two tubes for plasma and serum, respectively, at each sampling timepoint.

### Appendix 3 Pharmacokinetic and Biomarker Sampling Schedule (cont.)

#### Post-Induction Treatment (Eligible DLBCL Patients)

Study Visit	Serum Rituximab PK Sample a, b	Plasma Idasanutlin PK and Serum MIC-1 Sample c	Plasma Venetoclax PK Sample
Post-treatment	—	—	—
Treatment discontinuation	Any time during visit	—	—
120 days after the last dose	Any time during visit	—	—
1–2 years after the last dose	Any time during visit (if patient is in the clinic)	—	—

DLBCL = diffuse large B-cell lymphoma; PK = pharmacokinetic.

Note: A “—” indicates not applicable.

a Sample collection timing is relative to the specified drug.

b Samples collected for PK analysis may be used for additional PK, HACA, and/or ATA assay development and validation, and additional immunogenicity characterization, at the discretion of the clinical pharmacologist and/or the clinical scientist.

c Two tubes for plasma and serum, respectively, at each sampling timepoint.

## Appendix 4 Lugano Response Criteria for Malignant Lymphoma (Cheson et al. 2014)

In this study, the designation of a complete response (CR) using positron emission tomography–computed tomography (PET-CT)–based response requires normal bone marrow by morphology for patients with bone marrow involvement at baseline. If indeterminate by morphology, immunohistochemistry must be negative. Additionally, designation of PET-CT–based partial response (PR) requires that computed tomography (CT)-based response criteria for a CR or a PR be met in addition to the PET-CT–based response criteria for a PR.

Revised Criteria for Response Assessment		
Response and Site	PET-CT–Based Response	CT-Based Response
Complete	Complete metabolic response	Complete radiologic response (all of the following)
Lymph nodes and extralymphatic sites	Score 1, 2, or 3 a with or without a residual mass on 5PS b It is recognized that in Waldeyer’s ring or extranodal sites with high physiologic uptake or with activation within spleen or marrow (e.g., with chemotherapy or myeloid colony-stimulating factors), uptake may be greater than normal mediastinum and/or liver. In this circumstance, complete metabolic response may be inferred if uptake at sites of initial involvement is no greater than surrounding normal tissue even if the tissue has high physiologic uptake.	Target nodes/nodal masses must regress to $\leq 1.5$ cm in LDi No extralymphatic sites of disease
Non-measured lesion	Not applicable	Absent
Organ enlargement	Not applicable	Regress to normal
New lesions	None	None
Bone marrow	No evidence of FDG-avid disease in marrow	Normal by morphology; if indeterminate, IHC negative

## Appendix 4 Lugano Response Criteria for Malignant Lymphoma (Cheson et al. 2014) (cont.)

Revised Criteria for Response Assessment		
Response and Site	PET-CT–Based Response	CT-Based Response
Partial	Partial metabolic response	Partial remission (all of the following)
Lymph nodes and extralymphatic sites	Score 4 or 5 b with reduced uptake compared with baseline and residual mass(es) of any size	≥ 50% decrease in the sum of the product of the diameters SPD of up to 6 target measurable nodes and extranodal sites
	At interim, these findings suggest responding disease	When a lesion is too small to measure on CT, assign 5 mm × 5 mm as the default value
	At end of treatment, these findings indicate residual disease	When no longer visible, 0 × 0 mm
		For a node > 5 mm × 5 mm, but smaller than normal, use actual measurement for calculation
Non-measured lesion	Not applicable	Absent/normal, regressed, but no increase
Organ enlargement	Not applicable	Spleen must have regressed by > 50% in length beyond normal
New lesions	None	None
Bone marrow	Residual uptake higher than uptake in normal marrow but reduced compared with baseline (diffuse uptake compatible with reactive changes from chemotherapy allowed). If there are persistent focal changes in the marrow in the context of a nodal response, consideration should be given to further evaluation with MRI or biopsy or an interval scan.	Not applicable

**Appendix 4**  
**Lugano Response Criteria for Malignant Lymphoma**  
**(Cheson et al. 2014) (cont.)**

Revised Criteria for Response Assessment		
Response and Site	PET-CT–Based Response	CT-Based Response
No response or stable disease	No metabolic response	Stable disease
Target nodes/nodal masses, extranodal lesions	Score 4 or 5 b with no significant change in FDG uptake from baseline at interim or end of treatment	< 50% decrease from baseline in SPD of up to 6 dominant, measurable nodes and extranodal sites; no criteria for progressive disease are met
Non-measured lesion	Not applicable	No increase consistent with progression
Organ enlargement	Not applicable	No increase consistent with progression
New lesions	None	None
Bone marrow	No change from baseline	Not applicable

## Appendix 4 Lugano Response Criteria for Malignant Lymphoma (Cheson et al. 2014) (cont.)

Revised Criteria for Response Assessment		
Response and Site	PET-CT–Based Response	CT-Based Response

Progressive disease
 
Individual target nodes/nodal masses
 
Extranodal lesions
	
Progressive metabolic disease
 
Score 4 or 5b with an increase in intensity of uptake from baseline and/or
 
New FDG-avid foci consistent with lymphoma at interim or end-of-treatment assessment
	
Progressive disease requires at least 1 of the following PPD progression:
 
An individual node/lesion must be abnormal with: LDi > 1.5 cm and Increase by ≥ 50% from PPD nadir and An increase in LDi or SDi from nadir 0.5 cm for lesions ≤ 2 cm 1.0 cm for lesions > 2 cm
 
In the setting of splenomegaly, the splenic length must increase by > 50% of the extent of its prior increase beyond baseline (e.g., a 15-cm spleen must increase to > 16 cm). If no prior splenomegaly, must increase by at least 2 cm from baseline.
 
New or recurrent splenomegaly
 
New or clear progression of preexisting non-measured lesions

New lesions
	
New FDG-avid foci consistent with lymphoma rather than another etiology (e.g., infection, inflammation); if uncertain regarding etiology of new lesions, biopsy or interval scan may be considered
	
Regrowth of previously resolved lesions
 
A new node > 1.5 cm in any axis
 
A new extranodal site > 1.0 cm in any axis; if < 1.0 cm in any axis, its presence must be unequivocal and must be attributable to lymphoma
 
Assessable disease of any size unequivocally attributable to lymphoma

Bone marrow
	
New or recurrent FDG-avid foci
	
New or recurrent involvement

## Appendix 4 Lugano Response Criteria for Malignant Lymphoma (Cheson et al. 2014) (cont.)

---

5PS=5-point scale; CT=computed tomography; FDG=fluorodeoxyglucose; GI=gastrointestinal; IHC=immunohistochemistry; LDi=longest transverse diameter of a lesion; MRI=magnetic resonance imaging; PET=positron emission tomography; PPD=cross product of the LDi and perpendicular diameter; SDi=shortest axis perpendicular to the LDi; SPD=sum of the product of the perpendicular diameters for multiple lesions.

- a A score of 3 in many patients indicates a good prognosis with standard treatment, especially if at the time of an interim scan. However, in trials involving PET where de-escalation is investigated, it may be preferable to consider a score of 3 as inadequate response (to avoid undertreatment).  
Measured dominant lesions: Up to six of the largest dominant nodes, nodal masses, and extranodal lesions selected to be clearly measurable in two diameters. Nodes should preferably be from disparate regions of the body and should include, where applicable, mediastinal and retroperitoneal areas. Non-nodal lesions include those in solid organs (e.g., liver, spleen, kidneys, lungs), GI involvement, cutaneous lesions, or those noted on palpation. Non-measured lesions: Any disease not selected as measured; dominant disease and truly assessable disease should be considered not measured. These sites include any nodes, nodal masses, and extranodal sites not selected as dominant or measurable or that do not meet the requirements for measurability but are still considered abnormal, as well as truly assessable disease, which is any site of suspected disease that would be difficult to follow quantitatively with measurement, including pleural effusions, ascites, bone lesions, leptomeningeal disease, abdominal masses, and other lesions that cannot be confirmed and followed by imaging. In Waldeyer's ring or in extranodal sites (e.g., GI tract, liver, bone marrow), FDG uptake may be greater than in the mediastinum with complete metabolic response, but should be no higher than surrounding normal physiologic uptake (e.g., with marrow activation as a result of chemotherapy or myeloid growth factors).
- b PET 5PS: 1=no uptake above background; 2=uptake  $\leq$  mediastinum; 3=uptake  $>$  mediastinum but  $\leq$  liver; 4=uptake moderately  $>$  liver; 5=uptake markedly higher than liver and/or new lesions; X=new areas of uptake unlikely to be related to lymphoma.

## Appendix 5

### Classification of Tumor Lysis Syndrome Based on Howard Definition

To qualify for laboratory tumor lysis syndrome (TLS), a patient must have two or more metabolic abnormalities as defined in [Table 1](#) during the same 24-hour period within 3 days before the start of therapy or up to 7 days afterward (TLS risk decreases along treatment cycles). To qualify for clinical TLS, a patient must qualify for laboratory tumor lysis syndrome and have clinical signs of hyperkalemia, hypocalcemia, or acute kidney injury, such as (but not limited to) oliguria, increased creatinine, seizures, cardiac dysrhythmia, or death.

**Table 1 Criteria for Classification of Laboratory and Clinical Tumor Lysis Syndrome**

Metabolic Abnormality	Criteria for Classification of Laboratory Tumor Lysis Syndrome a	Criteria for Classification of Clinical Tumor Lysis Syndrome b
Hyperuricemia	Uric acid > 8.0 mg/dL (475.8 μmol/L) in adults or above the upper limit of the normal range for age in children	Not applicable
Hyperphosphatemia	Phosphorus > 4.5 mg/dL (1.5 μmol/L) in adults or > 6.5 mg/dL (2.1 μmol/L) in children	Not applicable
Hyperkalemia	Potassium > 6.0 μmol/L	Cardiac dysrhythmia or sudden death probably or definitely caused by hyperkalemia
Hypocalcemia	Corrected calcium < 7.0 mg/dL (1.75 μmol/L) or ionized calcium < 1.12 (0.3 μmol/L) c	Cardiac dysrhythmia, sudden death, seizures, neuromuscular irritability (tetany, paresthesias, muscle twitching, carpopedal spasm, Trousseau's sign, Chvostek's sign, laryngospasm, or bronchospasm), hypotension, or heart failure probably or definitely caused by hypocalcemia
Acute kidney injury c	Not applicable	Increase from baseline creatinine of ≥ 0.3 mg/dL (26.5 μmol/L), anuria, oliguria (defined as an average urine output of < 0.5 mL/kg/hr for 6 hours or more), or other clinical symptoms indicative of acute kidney injury

Source: Howard SC, Jones P, Pui CH. The tumor lysis syndrome. *N Engl J Med* 2011;12;364:1844–54.

a To qualify for laboratory tumor lysis syndrome, a patient must have two or more metabolic abnormalities during the same 24-hour period within 3 days before the start of therapy or up to 7 days afterward.

b To qualify for clinical tumor lysis syndrome, a patient must qualify for laboratory tumor lysis syndrome and have clinical signs of hyperkalemia, hypocalcemia, or acute kidney injury, such as (but not limited to) oliguria, increased creatinine, seizures, cardiac dysrhythmia, or death.

[figure not shown]
c Corrected calcium (mg/dL) = measured calcium (mg/dL) + 0.8 × (4 – albumin [g/dL]).

## Appendix 6

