### Recommendations for Initial Management of Electrolyte Imbalances and Prevention of Tumor Lysis Syndrome in the Setting of Treatment with Venetoclax (cont.)

Abnormality	Management Recommendations
Hyperkalemia (including rapidly rising potassium)	
Potassium greater than the ULN	
 
• Perform ECG immediately and commence telemetry.
 
• Perform nephrology assessment with consideration of initiating dialysis.
 
• Administer Kayexalate® 60 g (or Resonium A® 60 g).
 
• Administer furosemide 20 mg IV × 1.
 
• Administer calcium gluconate 100–200 mg/kg IV slowly if there is ECG or telemetry evidence of life-threatening arrhythmias.
 
• Recheck potassium, phosphorus, uric acid, calcium, and creatinine in 1 hour STAT.
 
• If potassium is less than the ULN 1 hour later, repeat potassium, phosphorus, uric acid, calcium, and creatinine 1, 2, and 4 hours later if no other evidence of tumor lysis.
 

Potassium ≥0.5 µmol/L increase from prior value (even if potassium is WNL)	
 
• Recheck potassium, phosphorus, uric acid, calcium, and creatinine in 1 hour STAT. If there is a further increase ≥0.2 µmol/L in potassium, but still less than the ULN, manage per potassium greater than the ULN. Otherwise, recheck in 1 hour.
 
• Resume per protocol testing if change in potassium is <0.2 µmol/L and potassium is less than the ULN and no other evidence of tumor lysis.
 
• At the discretion of the investigator, may recheck before hospitalization. If potassium is stable or decreased and still WNL, hospitalization will be at the discretion of the investigator. Potassium, phosphorus, uric acid, calcium, and creatinine must be rechecked within 24 hours.
 

ECG=electrocardiogram; IV=intravenous; STAT=immediately; ULN=upper limit of normal; WNL=within normal limit.

## Appendix 12

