### Recommendations for Initial Management of Electrolyte Imbalances and Prevention of Tumor Lysis Syndrome in the Setting of Treatment with Venetoclax (cont.)

Abnormality	Management Recommendations

Hyperkalemia (including rapidly rising potassium) (cont.)
 
Potassium <math>\geq 6.0</math> <math>\mu\text{mol/L}</math> (6.0 mEq/L) and/or patient is symptomatic (e.g., muscle cramps, weakness, paresthesias, nausea, vomiting, and diarrhea)
	
 
• Perform STAT ECG and commence telemetry.
 
• Perform nephrology assessment with consideration of initiating dialysis.
 
• Administer Kayexalate® 60 g (or Resonium A® 60 g).
 
• Administer furosemide 20 mg IV <math>\times 1</math>.
 
• Administer insulin 0.1 U/kg IV + D25 2 mL/kg IV.
 
• Administer sodium bicarbonate 1–2 mEq by IV push. If sodium bicarbonate is used, rasburicase should not be used as this may exacerbate calcium phosphate precipitation.
 
• Administer calcium gluconate 100–200 mg/kg IV slowly if there is ECG or telemetry evidence of life-threatening arrhythmias. Do not administer in same IV line as sodium bicarbonate.
 
• Recheck potassium, phosphorus, uric acid, calcium, and creatinine every hour STAT.
 

Hyperuricemia
 
Uric acid <math>\geq 8.0</math> mg/dL (476 <math>\mu\text{mol/L}</math>)
	
 
• Consider rasburicase (dose per institutional guidelines). If rasburicase is used, sodium bicarbonate should not be used as this may exacerbate calcium phosphate precipitation.
 
• Recheck potassium, phosphorus, uric acid, calcium, and creatinine in 1 hour STAT.
 

ECG=electrocardiogram; IV=intravenous; STAT=immediately; ULN=upper limit of normal; WNL=within normal limit.

## Appendix 12

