### Recommendations for Initial Management of Electrolyte Imbalances and Prevention of Tumor Lysis Syndrome in the Setting of Treatment with Venetoclax (cont.)

Abnormality	Management Recommendations

Hyperuricemia (cont.)
 
Uric acid <math>\geq 10</math> mg/dL (595 <math>\mu\text{mol/L}</math>)  or            uric acid <math>\geq 8.0</math> mg/dL (476 <math>\mu\text{mol/L}</math>) with 25% increase and creatinine increase <math>\geq 0.3</math> mg/dL (<math>\geq 0.027</math> <math>\mu\text{mol/L}</math>) from pre-dose level
	
 
• Administer rasburicase (dose per institutional guidelines).
 
If rasburicase is used, sodium bicarbonate should not be used as this may exacerbate calcium phosphate precipitation.
 
• Consult nephrology.
 
• Recheck potassium, phosphorus, uric acid, calcium, and creatinine in 1 hour STAT.
 
• If uric acid <math>< 8.0</math> mg/dL 1 hour later, repeat potassium, phosphorus, uric acid, calcium, and creatinine 2 and 4 hours later if no other evidence of tumor lysis.
 

Hypocalcemia
 
Calcium <math>\leq 7.0</math> mg/dL (1.75 <math>\mu\text{mol/L}</math>)  and            patient is symptomatic (e.g., muscle cramps, hypotension, tetany, cardiac arrhythmias)
	
 
• Administer calcium gluconate 50–100 mg/kg IV slowly with ECG monitoring.
 
• Perform telemetry.
 
• Recheck potassium, phosphorus, uric acid, calcium, and creatinine in 1 hour STAT.
 
• If calcium normalized 1 hour later, repeat potassium, phosphorus, uric acid, calcium, and creatinine 2 and 4 hours later if no other evidence of tumor lysis.
 
• Calculate corrected calcium and check ionized calcium if albumin is low.
 

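### Minor, subject to a check of the source PDF: Appendices 5 and 12 print 13 potassium, phosphorus, calcium and creatinine limits in μmol/L whose values are in mmol/L; a 14th, ionized calcium, is also wrong but cannot be resolved from the documents

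*Protocol*

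**What the plan says.** Appendix 5, Table 1 lists the metabolic abnormalities that make up laboratory TLS. Its phosphorus entry reads "Phosphorus > 4.5 mg/dL (1.5 μmol/L) in adults or > 6.5 mg/dL (2.1 μmol/L) in children". Its potassium entry is "Potassium > 6.0 μmol/L", with no conventional value beside it. Its calcium entry reads "Corrected calcium < 7.0 mg/dL (1.75 μmol/L) or ionized calcium < 1.12 (0.3 μmol/L"), and the 1.12 has no unit. The kidney-injury row reads "Increase from baseline creatinine of ≥ 0.3 mg/dL (26.5 μmol/L").

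Appendix 12 sets the limits for action after a venetoclax dose:

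- **Potassium, within 24 hours.** One hyperkalemia row begins "Potassium ≥0.5 µmol/L increase from prior value (even if potassium is WNL"). If a recheck shows a further rise of 0.2 μmol/L, the instruction continues "in potassium, but still less than the ULN, manage per potassium greater than the ULN". A change below 0.2 μmol/L allows routine testing to resume. A separate row pairs a level of 6.0 μmol/L with 6.0 mEq/L.
- **Potassium, ongoing dosing.** A rise of 1.0 μmol/L is paired with 1.0 mEq/L.
- **Phosphorus.** A level of 5.0 mg/dL is given as 1.615 μmol/L, and a rise of 0.5 mg/dL as 0.16 μmol/L.
- **Calcium.** 7.0 mg/dL is given as 1.75 μmol/L.
- **Creatinine.** A rise of 0.3 mg/dL is given as 0.027 μmol/L.

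**The concern.** The protocol contradicts itself on these units. One mEq/L of potassium, a monovalent ion, is 1 mmol/L, so 6.0 μmol/L cannot equal 6.0 mEq/L. The same creatinine rise cannot be both 26.5 and 0.027 μmol/L.

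The tables are operating instructions. Sections 5.1.6 and 5.1.7.2 send sites to Appendix 12. Its criteria for the first 24 hours lead to admission and a hold on venetoclax. Table 18 withholds study treatment for laboratory TLS of Grade 3 or lower.

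Taken literally, the adult potassium and phosphorus levels are always exceeded and the SI calcium limits are never met. Almost any rise meets the change limits, while the below-0.2 condition for resuming routine testing needs essentially no rise.

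The entries with most practical weight are the unpaired potassium changes in Appendix 12. They apply to patients whose potassium is normal, and a small further rise moves the patient to the treatment list for potassium above the upper limit of normal. A very small change limit is also less obviously absurd than a potassium level of 6.0 μmol/L.

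**Working it through.** **Inputs.** The limits are those printed in Appendix 5, Table 1 and Appendix 12. Molar masses (g/mol): phosphorus 30.974, calcium 40.078, creatinine 113.12, uric acid 168.11.

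**Formula.** μmol/L = mg/dL × 10,000 / molar mass. For potassium, 1 mEq/L = 1 mmol/L = 1000 μmol/L.

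**Controls, where the print is right.** Uric acid 8.0 mg/dL gives 475.9 μmol/L (printed 475.8 and 476), and 10 mg/dL gives 594.8 (printed 595). Creatinine 0.3 mg/dL gives 26.5 (printed 26.5 in Appendix 5).

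**Paired limits, where it is not.**

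| Limit | Conventional | Correct μmol/L | Printed μmol/L | Ratio |
|---|---|---|---|---|
| Phosphorus, App. 5, adults | 4.5 mg/dL | 1452.8 | 1.5 | 969 |
| Phosphorus, App. 5, children | 6.5 mg/dL | 2098.5 | 2.1 | 999 |
| Phosphorus level, App. 12 | 5.0 mg/dL | 1614.3 | 1.615 | 1000 |
| Phosphorus rise, App. 12 | 0.5 mg/dL | 161.4 | 0.16 | 1009 |
| Calcium, App. 5 and App. 12 | 7.0 mg/dL | 1746.6 | 1.75 | 998 |
| Potassium level, App. 12 | 6.0 mEq/L | 6000 | 6.0 | 1000 |
| Potassium rise, App. 12 | 1.0 mEq/L | 1000 | 1.0 | 1000 |
| Creatinine rise, App. 12 | 0.3 mg/dL | 26.5 | 0.027 | 981 |

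The departures from 1000 are rounding in the printed values. Read as mmol/L, every figure agrees with its partner.

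**Creatinine from the protocol's own constants.** Comparing the two Cockcroft-Gault forms in Appendix 11 gives 1.23 × 72 = 88.56 (male) and 1.04 × 72 / 0.85 = 88.09 (female) μmol/L per mg/dL. A rise of 0.3 mg/dL is therefore 26.4 to 26.6 μmol/L, which supports Appendix 5 against Appendix 12.

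**Unpaired potassium.** Appendix 5 (6.0) and Appendix 12 (0.5, 0.2, 0.2) give no conventional value, but the 6.0 and 1.0 mEq/L pairings elsewhere in Appendix 12 show the scale.

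**Ionized calcium.** If 1.12 is in mg/dL it equals 279 μmol/L; in mEq/L, 560; in mmol/L, 1120. None equals 0.3 μmol/L. Only the mg/dL reading (0.279 mmol/L) makes 0.3 a millimolar value. Under the other two, 0.3 is a wrong number rather than a wrong unit.

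**Count.** Appendix 5 has five affected labels and Appendix 12 has nine, so 14. By analyte: potassium 6, phosphorus 4, total or corrected calcium 2, creatinine 1, ionized calcium 1. Leaving out ionized calcium, 13 are established. Of the 14, nine carry a labelled conventional value, one an unlabelled number, and four nothing.

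**Literal reading of the potassium changes.** Assume laboratories report potassium in steps of 0.01 to 0.1 mmol/L, that is 10 to 100 μmol/L. The smallest reportable rise is then 10/0.5 = 20 to 100/0.5 = 200 times the 0.5 limit, and 10/0.2 = 50 to 100/0.2 = 500 times the 0.2 limit.

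**The case against.** The strongest reply is that this may not be the sponsor's error. If mmol/L was misread as μmol/L throughout when the PDF was turned into text, the result would be exactly this pattern, creatinine contradiction included. Neither appendix contains a mmol/L that would show the string being read correctly, and the μ appears in several typographic forms. This stands far enough that the source PDF must be checked first. It does not remove the point. Fourteen identical substitutions across differently rendered strings in two appendices are improbable, and millimetres in Appendix 4, mEq/L and the true micromolar values all read properly.

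The second reply is that nobody would act on the literal figures. Nine limits carry a labelled conventional value, and Appendix 12 lets the investigator recheck a potassium rise before admitting the patient. Laboratory TLS needs two abnormalities within the same 24 hours. The 2.1 phosphorus limit is for children, who cannot enrol. The creatinine limit only turns optional rasburicase into required rasburicase, with a nephrology consult, for a patient whose uric acid is already at least 8.0 mg/dL and up by 25%. All of this stands, and it is why the point is minor.

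A reader might infer that all 14 labels can simply be changed to mmol/L. The documents do not support that for ionized calcium.

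**Conclusion.** As the text stands, 13 limits in Appendices 5 and 12 carry the wrong unit by a factor of 1000. The ionized calcium limit is also wrong in μmol/L, in a way the documents cannot resolve. The finding rests on standard molar masses and on the print matching the source PDF. Severity is minor.

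A reader might go further and infer that DLT calls or trial results are distorted. The documents do not support that. Protocol Section 3.1.2.1 exempts Grade 3 laboratory TLS without clinical TLS from the DLT definition, and counts adverse events of any grade that delay the next cycle by more than 14 days under a separate rule. SAP Section 6.2.2 identifies TLS by preferred term, so no SAP derivation uses these limits. No endpoint or sample size depends on them.

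Nor do the documents show that patients would be managed on the literal figures. The point is that safety instructions should not contradict themselves, above all where no conventional value sits beside the limit.

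**What to change.** Check both appendices against the source PDF. If the print is confirmed:

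1. Change μmol/L to mmol/L for 12 limits: potassium (6.0 in each appendix, 0.5, 0.2 twice, 1.0), phosphorus (1.5, 2.1, 1.615, 0.16) and calcium (1.75 in each appendix). Start with the four unpaired potassium limits, and consider adding mEq/L beside them.
2. Print the Appendix 12 creatinine rise as 26.5 μmol/L, to match Appendix 5.
3. For ionized calcium, consult the TLS definition cited under the Appendix 5 table, then correct the units of both 1.12 and 0.3 together.

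The cost is a set of label corrections in two appendices, by clarification letter or in the next amendment. Design, analysis and SAP programming do not change.
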